19.1.1.4 Monitoring of Data

- (1) Responsible parties for data and safety monitoring: As the PI for the trial, [name] will be responsible for ensuring trial participants' safety on a daily basis. Both the Chief of Cardiac Anesthesiology at PPMC, [name], and the Chief of Cardiac Surgery, [name], will be updated on the trial safety (including incidences of AEs/SAEs). The DSMB will act in an advisory capacity to monitor trial participants' safety, evaluate the progress of the study, review procedures to maintain confidentiality, review the quality of the data collected, management of the data, and the plans for data analyses.
- (2) Frequency of data and safety monitoring: In addition to daily safety monitoring, [name] will also perform weekly data audits to ensure the highest standards for data integrity. Specifically, this will involve checks to ensure complete data collection, identify data inaccuracies, and perform EMR audits to ensure data is

Clinical Study Number:	NCT06154265	Document Title:	10/24/2024	Page 30 of 36
		Default vs As-Needed Intraoperative Transesophageal Echocardiography (TEE) in Low-Risk Isolated Coronary Artery Bypass Graft (CABG) Surgery: A Randomized Controlled Trial		

being correctly collected. Any data problems will be identified and corrected either by [name] or by research staff. Logs of these data issues will be maintained to keep a record of problem areas with specific variables or with individual research team members to allow [name] and the DSMB to proactively modify data collection procedures or re-train research team members. Logs of communications with study staff regarding data cleaning and management will also be maintained to keep track of corrected issues. [name] will provide a weekly, trial safety report to both [name] (Chief of Cardiac Anesthesiology at PPMC) and mentor, [name] (Chief of Cardiac Surgery at PPMC). The DSMB will annually, either in-person or by teleconference call to review study progress, data quality and participant safety alongside [name]. Written safety reports will be sent to the both the UPenn IRB and the NHLBI Program Officer annually to provide detailed information on trial progress, safety issues, data collection, data management, and analysis.

- (3) Content of Data and Safety Monitoring Report: The written progress report submitted to the DSMB, UPenn IRB, NHLBI Program Officer will include: (a) trial status dates and checkpoints; (b) reports on data completeness; (c) logs of AEs/SAEs; (d) logs of changes to the trial protocol; (e) anticipated trial timeline and deadlines for trial deliverables.
- (4) DSMB Membership and Affiliation: DSMB members will be identified prior to start of the RCT. DSMB membership will be sent to the NHLBI. Should there be any questions regarding the independence of the DSMB, it will be addressed and corrected if necessary.
- (5) Conflict of Interest for DSMB: The DSMB should have no direct involvement with the study investigators or intervention. Each DSMB member will sign a Conflict of Interest Statement which includes current affiliations, if any, with pharmaceutical and biotechnology companies (e.g., stockholder, consultant), and any other relationship that could be perceived as a conflict of interest related to the trial and/or associated with commercial interest pertinent to RCT objectives.
- (6) Responsibilities of the DSMB:
 - a. Review the trial protocol, informed consent documents and plans for data safety and monitoring.
 - b. Evaluate the progress of the trial, including periodic assessments of data quality and timeliness, recruitment, accrual and retention, participant risk vs benefit, performance for the trials sites, and other factors potentially affecting study outcomes.
 - c. Consider factors external to the study when relevant information becomes available, such as scientific or therapeutic developments that may have an impact on the safety of the participants or the ethics of the trial.
 - d. Review study performance, make recommendations and assist in the resolution of problems reported by [name]
 - e. Protect the safety of the study participants.
 - f. Report to NHLBI on the safety and progress of the trial.

Clinical Study Number:	NCT06154265	Document Title:	10/24/2024	Page 31 of 36
		Default vs As-Needed Intraoperative Transesophageal Echocardiography (TEE) in Low-Risk Isolated Coronary Artery Bypass Graft (CABG) Surgery: A Randomized Controlled Trial		

- g. Make recommendations to the NHLBI and the PI ([name]) concerning continuation, termination or other modifications of the trial based on the observed beneficial or adverse effects of intraoperative TEE as proposed in the trial protocol.
- h. If appropriate, review interim analyses in accordance with stopping rules, which are clearly defined in advance of data analysis and have the approval of the DSMB.
- i. Ensure the confidentiality of the study data and the results of monitoring.
- j. Assist the NHLBI by commenting on any problems with study conduct or enrollment.

Clinical Study Number:	NCT06154265	Document Title:	10/24/2024	Page 32 of 36
		Default vs As-Needed Intraoperative Transesophageal Echocardiography (TEE) in Low-Risk Isolated Coronary Artery Bypass Graft (CABG) Surgery: A Randomized Controlled Trial		

19.2 Recruitment and Retention Plan

19.2.1 Recruitment Plan

- Recruitment for the randomized controlled trial (RCT) will occur through the Penn Presbyterian Medical Center (PPMC) cardiac surgery clinic of the University of Pennsylvania Health System. Within our Institutional Review Board (IRB) protocol, we will request permission to access clinic and surgical schedules of potential isolated coronary artery bypass graft (CABG) patients in order to identify potential RCT subjects that meet inclusion and exclusion criteria for enrollment in the trial. Once a potential subject has been identified, he or she will be approached in-person, pre-procedure. After a brief introduction, either the research assistant (RA) or the principal investigator (PI) will approach these patient participants and ask if they would be interested in hearing about the trial. If they agree, the RA or PI will ask a series of additional screening questions to confirm that the patient meets eligibility criteria. If the patient is deemed eligible and expresses interest in learning more about the study, the RA or PI will review the intent of the study, present the current data regarding risks and benefits to using intraoperative transesophageal echocardiography (TEE) during isolated CABG surgery. Once the patient agrees to participate, the RA or PI will complete the enrollment process by providing an information packet, collecting basic demographic and health data, reviewing study timeline and protocols, and obtaining written informed consent that confirms the study subjects' agreement to participate in the RCT as specified in the trial protocol and the subjects' permission to allow the research team to access electronic medical records. Patients will receive an incentive for completing all phases of the study. The trial inclusion and exclusion criteria for subject participation listed in the above-protocol will be confirmed and finalized with [name] prior to initiation of recruitment.

19.2.1.1 Estimated Rates of RCT Enrollment

- We will recruit up to 75 isolated CABG surgery patients who present to the cardiac surgery clinic(s) at either PPMC or the Hospital of the University of Pennsylvania. The Division of Cardiovascular Surgery, within the University of Pennsylvania Health System is the largest cardiac surgery division in the State of Pennsylvania and receives over 250 isolated CABG referrals per year. This breaks down to approximately 20 patients per month. Assuming half of these patients meet inclusion criteria (i.e. 10 potential subjects per month), to meet our sample size of 22 isolated CABG surgery patients in year, we would need a 20% participation rate over 12 months; equating to approximately 2 – 3 study subjects per month. Although we do not anticipate difficulty in recruitment, if we are unable to achieve our

Clinical Study Number:	NCT06154265	Document Title:	10/24/2024	Page 33 of 36
		Default vs As-Needed Intraoperative Transesophageal Echocardiography (TEE) in Low-Risk Isolated Coronary Artery Bypass Graft (CABG) Surgery: A Randomized Controlled Trial		

projected sample size goal within one year, we will extend the recruitment period six months.

19.2.1.2 Optimizing RCT Recruitment Strategy for Future Multicenter RCT

- Throughout the execution of this RCT, we will continually assess and document rates of recruitment of eligible participants to inform project timelines and improve our recruitment strategy for a future, multicenter, RCT. In particular, we will evaluate whether the verbal consent discussion and written materials provided to patients during the initial encounter were satisfactory and understandable to participating study subjects or whether additional improvements could be made to allow for higher study participation rates in the future

19.2.2 RCT Retention Plan

- To ensure optimal retention of RCT participants, we will follow an enhanced retention approach that includes collecting contact information (e.g. physical address, mobile phone numbers, email address, etc.) from each participant. We will also ask the participant to designate one other individual to allow researchers to locate and communicate with participants in the event that the participant cannot be reached directly.
- During the trial, the RCT protocol will involve a member of the research team conducting in-person interviews post-CABG surgery with each study participant. Interview questions will cover incidence of clinical adverse sequelae (e.g. difficulty or painful swallowing, hoarseness, etc.) in each trial arm and will also involve asking open-ended questions regarding the study protocol to allow participants to provide feedback to research team personnel on how to optimize the study protocol for participating subjects. We will encourage study participants to consider themselves essential members of the study team with valuable information that is critical to the success of a future trial. At the end of the study, we will invite patients to consider staying on as representative stakeholders to serve on a monitoring board for a future, multicenter RCT comparing default vs as-needed intraoperative TEE during isolated CABG surgery.
- During the course of the study, we will encourage patients to directly contact research team personnel or the PI ([name]) at any point before, during, or following RCT completion. To facilitate this level of open communication, participating RCT subjects will be provided the PI ([name]'s) mobile phone number in the information packet. Subjects will be told they can contact the PI directly 24/7 to answer questions or address concerns regarding RCT participation.

Clinical Study Number:	NCT06154265	Document Title:	10/24/2024	Page 34 of 36
		Default vs As-Needed Intraoperative Transesophageal Echocardiography (TEE) in Low-Risk Isolated Coronary Artery Bypass Graft (CABG) Surgery: A Randomized Controlled Trial		

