6.2 Secondary Objective(s)

- Describe the incidence of gastroesophageal symptoms, injury, or complications: defined as the rate of patient-reported gastroesophageal symptoms (e.g. painful or difficulty swallowing, hoarseness, or eating), swallowing dysfunction (defined by the need for a postoperative swallowing evaluation after surgery), or diagnosis of a new gastroesophageal problem (defined by the need for an upper endoscopy after surgery).

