8.5.2 Survey Data Collection

- The PI ([name]) or other IRB-approved research personnel will conduct two interviews with the patient: (1) the first interview will occur following extubation (i.e. removal of the breathing tube after CABG surgery) within a 6 – 24 hour post-surgical window; (2) the second interview will occur at any point between 1 – 5 days post-surgery. These interviews will take approximately 15 – 30 minutes.

Clinical Study Number:	NCT06154265	Document Title:	10/24/2024	Page 16 of 36
		Default vs As-Needed Intraoperative Transesophageal Echocardiography (TEE) in Low-Risk Isolated Coronary Artery Bypass Graft (CABG) Surgery: A Randomized Controlled Trial		

- No identifying information from the patient will be collected. Survey data will be labeled only by subject number.
- Patient Interview Questions
 - 1. Did you, or do you currently have symptoms of throat soreness?
 - 2. Does your throat feel dry or scratchy?
 - 3. Have you had difficulty swallowing liquids, pills, or food?
 - 4. Has swallowing been painful?
 - 5. Have you felt nauseous or vomited?
 - 6. Have you had symptoms of acid reflux?
 - 7. Did you ever have the taste of blood in your mouth?
 - 8. Have you had any GI symptoms I haven't asked you about?

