10.2 Secondary Endpoint Analysis

Although this study is not powered to detect a difference in clinical outcomes between the default and as-needed intraoperative TEE groups, to plan for a future RCT that would be powered to detect a difference in clinical outcomes. We will collect clinical data on gastroesophageal dysfunction (symptoms or injury), incidence of end-organ dysfunction, and incidence of death as defined by the following:

1. Evidence of clinically-significant gastroesophageal dysfunction during hospitalization – either by patient-reported symptoms or by the presence of testing for swallowing difficulty, dysfunction, or upper endoscopy diagnostic procedures.
2. Evidence of end-organ dysfunction based on clinical notes (e.g. “transaminitis,” “acute kidney/renal injury”), and/or laboratory-based evidence of (e.g. liver function tests [LFTs], serum creatinine [Cr], lactate, etc.).
3. Incidence of in-hospital, post-surgical, cardiovascular re-intervention (e.g. return to the operating room for any reason, unplanned or emergency cardiac catheterization post-surgery, or placement on venoarterial extracorporeal membrane oxygenation [VAECMO]).
4. Incidence of all-cause in-hospital mortality

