19.1 Data Safety and Monitoring Plan

19.1.1 Adverse Event (AE) and Serious Adverse Event (SAE) Collection and Reporting

19.1.1.1 Safety Monitoring Definitions and list of AEs and SAEs to be tracked

- (1) Adverse Event (AE) – Any untoward or unfavorable medical occurrence in a human subject, including any abnormal sign, symptom, or disease process, temporally associated with the subject's participation in the research, whether or not considered directly-related to the subject's participation in the research. The itemized list of adverse events we will track is provided in this section (subsection 5).
 - a. Clinically-significant but non-life threatening gastroesophageal complications possibly related to transesophageal echocardiography (TEE).
 - b. Cardiovascular complications after isolated CABG surgery.
 - c. Breach of confidentiality.
- (2) Serious Adverse Event (SAE) – Any AE that results in death or a life-threatening AE.
- (3) List of AEs and SAEs (severity of which will be assessed on a case-by-case basis)
 - a. Death
 - b. New myocardial infarction (MI) post-surgery
 - c. Unplanned post-surgery percutaneous coronary intervention (PCI)
 - d. Unplanned CABG surgery revision
 - e. Unplanned open valve repair or replacement
 - f. Stroke
 - g. Transient ischemic attack (TIA)
 - h. Return to operating room for bleeding
 - i. Cardiac tamponade
 - j. Pericardial effusion
 - k. Prolonged intubation (defined as >48 hours of mechanical ventilatory support)
 - l. Pneumonia
 - m. Surgical site infection
 - n. Unplanned ICD or pacemaker insertion post-surgery
 - o. Post-surgery angina
 - p. New-onset atrial fibrillation
 - q. Pulmonary embolism (PE)

Clinical Study Number:	NCT06154265	Document Title:	10/24/2024	Page 28 of 36
		Default vs As-Needed Intraoperative Transesophageal Echocardiography (TEE) in Low-Risk Isolated Coronary Artery Bypass Graft (CABG) Surgery: A Randomized Controlled Trial		

- r. Deep vein thrombosis (DVT)
 - s. Gastrointestinal or esophageal complication requiring diagnostic testing
 - t. Failed swallow evaluation

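### The postoperative interview omits hoarseness, has no baseline or scoring rule, and sets a first window that late-extubated patients cannot meet, so the symptom part of the gastroesophageal endpoint is measured incompletely and non-specifically

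*Combined protocol and SAP*

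**What the plan says.** - **Endpoint.** Section 6.2 sets out to describe incidence and gives as examples of patient-reported symptoms "e.g. painful or difficulty swallowing, hoarseness, or eating". Its other components are the need for a postoperative swallowing evaluation and the need for an upper endoscopy.
- **Endpoint as worded in the Synopsis and Section 10.2.** The dysfunction is labelled clinically significant, and is established "either by patient-reported symptoms or by the presence of testing for swallowing difficulty, dysfunction, or upper endoscopy diagnostic procedures". Section 10.2 says the clinical data are collected to plan a later, powered trial.
- **Promise about the interview.** Section 19.2.2: "Interview questions will cover incidence of clinical adverse sequelae (e.g. difficulty or painful swallowing, hoarseness, etc.) in each trial arm".
- **Questions.** Section 8.5.2 lists eight: throat soreness; dry or scratchy throat; swallowing difficulty ("Have you had difficulty swallowing liquids, pills, or food"); painful swallowing; nausea or vomiting; acid reflux; taste of blood; and an open item limited to other GI symptoms.
- **Timing.** Interview 1 takes place after extubation and "within a 6 – 24 hour post-surgical window". For the other, "the second interview will occur at any point between 1 – 5 days post-surgery". Section 12 makes an interview outside its window a protocol deviation.
- **Late extubation is foreseen.** The event list in Section 19.1.1.1 includes ventilation for more than 48 hours and, separately, a failed swallow evaluation.

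**The concern.** The interview is the only planned source of patient-reported symptoms, and it does not match the endpoint it supplies. One named symptom is not asked about. Existing symptoms cannot be told from new ones. Nothing says which answers count, although several items (dry throat, nausea) could arise from intubation and anesthesia, which both arms share. For a patient still intubated at 24 h, interview 1 must be either missed or recorded as a deviation.

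What is at stake is the rate carried into the next trial. Gastroesophageal injury is one of three trial outcomes in the Synopsis overview, and it is the only secondary objective in Section 6.2. A rate that omits a named symptom and mixes in background complaints would mislead the sizing of that trial.

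**Working it through.** The documents give no symptom rate and no power calculation for this endpoint, so there is no figure to reproduce. The check compares the sections; the arithmetic after it is illustrative.

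**1. Named symptoms against the questions**
- Difficult swallowing: question 3.
- Painful swallowing: question 4.
- Difficulty eating: only partly, through the mention of food in question 3.
- Hoarseness: no question. Question 8 invites other GI symptoms and does not prompt for voice change.

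**2. Baseline**
- Both interviews follow surgery. Preoperative information comes from the medical record (Sections 8.5.1 and 15.1) and from basic health data at enrollment (Section 19.2.1).
- No symptom interview precedes surgery. The exclusions in Section 6.3.2 cover several esophageal conditions, but not reflux or ordinary dysphagia.
- A patient with long-standing reflux can truthfully answer yes to question 6.
- Arms are randomized, so this does not bias the comparison systematically. It raises the absolute rate and leaves chance imbalance. For a pre-existing symptom with an assumed prevalence of 10% to 50%, the exact binomial chance that the arms differ by 20 points or more is 2.4% to 17.4% with 22 per arm (Section 10.3). It is 7.2% to 28.6% with 11 per arm (Section 19.5.2's total of 22, assuming 1:1 allocation).

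**3. Scoring rule**
- Neither the Synopsis nor Section 10.2 lists qualifying items, a severity threshold, or a rule for combining the two interviews. All patients are intubated before randomization (Section 8.4.1).
- The range left open can be shown with an assumed rate r per item and independent items. P(any of 8) = 1 − (1 − r)^8; P(question 3 or 4) = 1 − (1 − r)^2.
  - r = 5%: 34% and 10%
  - r = 10%: 57% and 19%
  - r = 20%: 83% and 36%
- Overlapping items are probably correlated. With an assumed latent correlation of 0.5, the r = 20% figures fall to 58% and 31%.

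**4. Dilution**
- Let b be an assumed background rate common to both arms, and t the TEE effect. Take t = 4%, the top of the 0.1%–4% injury range in Section 11.1; applying it to symptoms is itself an assumption. Assume no TEE in the as-needed arm. Then p(default) = b + (1 − b)t and p(as-needed) = b.
- b = 5%: 0.05 + 0.95 × 0.04 = 8.8%; difference 3.8 points; share of default-arm positives due to TEE 3.8/8.8 = 43%.
- b = 50%: 0.50 + 0.50 × 0.04 = 52%; difference 2.0 points; share 2.0/52 = 3.8%.
- Size of a future trial: n per arm = [1.96√(2p̄(1 − p̄)) + 0.8416√(p₁(1 − p₁) + p₂(1 − p₂))]² / (p₁ − p₂)², for 80% power and an assumed two-sided 5% level. This gives 698 at b = 5% and 9,806 at b = 50%.

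**5. Interview 1 window**
- Extubation after 24 h and an interview by 24 h cannot both hold. If 1%, 5% or 10% of patients (assumed) are intubated beyond 24 h, expected misses are 0.4, 2.2 or 4.4 of 44 patients, or 0.2, 1.1 or 2.2 of 22.

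**6. Testing**
- The record-based components turn on a test being needed or present, not on its result. A result-based measure, the failed swallow evaluation, is already tracked in Section 19.1.1.1.

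**The case against.** The strongest reply is that much of the endpoint is measured. Questions 3 and 4 ask directly about the first symptoms that Section 6.2 lists, and swallow evaluations and endoscopies come from the record. The trial is a feasibility study with process measures as primary endpoints, and it concedes that it is underpowered for clinical outcomes. This stands, and it limits the point to the symptom component. It does not supply the missing question, the baseline or the scoring rule.

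Four stronger readings are tempting but unsupported:

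- **That the endpoint cannot be measured, or that its rate is useless.** The sources just named contradict this, and items can be reported singly.
- **That any positive answer counts, so the composite saturates.** No section says so. Section 6.2's examples are swallowing, hoarseness and eating, not dry throat or nausea. The rule is left open, and the high rates above appear only under an assumed rule and assumed inputs.
- **That late-extubated patients are lost.** Only interview 1 is out of reach at 24 h. Interview 2 stays open through day 5, and several questions look back in time. Nothing in the documents shows that these patients are the likeliest to have dysphagia.
- **That tests are ordered by clinicians who know the arm, or that the missing baseline biases the comparison.** The documents describe no blinding, but they do not say what the staff ordering postoperative tests know. Randomization prevents systematic baseline bias.

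**Conclusion.** The point holds in a limited form. Three defects follow from the text alone: hoarseness is named and promised but not asked about; no symptom baseline supports a reported incidence; and interview 1 cannot be met after 24 h of intubation. A fourth is an omission: an endpoint labelled clinically significant has no list of qualifying symptoms and no severity rule, and it accepts the presence of testing without a result.

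The documents fix no size for the consequence. The dilution figures rest on assumed background rates, and the any-of-eight figures on assumed item rates and mainly on independence. They show direction only. The change should be made because the data are meant to inform a later trial, but it does not threaten this trial's primary endpoints.

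**What to change.** 1. Add a hoarseness question to Section 8.5.2.
2. Ask the same items once at the consent visit, and count only symptoms that are new or worse at either postoperative interview.
3. Base the symptom endpoint on the symptoms that Section 6.2 names: difficult swallowing, painful swallowing, hoarseness and difficulty eating. State the severity that counts, and report the other items singly.
4. Report test results, such as a failed swallow evaluation, separately from tests ordered.
5. Set interview 1 at 6–24 h after extubation. The Synopsis gives a 120-hour period from entry to the operating room; for patients extubated too late for two interviews within it, use a single interview. Extubation after hour 114 (120 − 6) leaves no time even for that, so report such patients as not assessed.
6. Narrowing the interview 2 window is optional. If a minimum gap is added, check it against the 120 hours: a 24 h gap after an interview at least 6 h from extubation fails for anyone extubated after about hour 90 (120 − 6 − 24).

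The cost is one extra question, a few minutes at the consent visit and amended text in Sections 6.2, 8.5.2 and 10.2. Treatment is unaffected.
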